Missing data. We expect to collect $\geq 85\%$ of the study assessments. Our primary approach to handle missing data will be to impute missing values as the adverse outcome (e.g., buprenorphine-negative urine sample). Model parameter estimates from this approach will be compared to a method without imputation. If these methods yield differing results, conclusions will need to be tentative, but results from both approaches will be reported in publications. To investigate sensitivity to missing values, participants with and without missing values will be compared by covariates and group assignment. If rates are higher than expected, we may use mixed effects models rather than GEE estimation, as the former has less strict assumptions regarding missing data (missing at random, rather than missing completely at random).

Power Analyses

We used Liu and Liang⁸⁴ to determine the number of participants required to detect a difference of 15% between groups using the three monthly assessments during the 3-month intervention period with 80% power and adjusting for missing data (15% missing). Based on these analyses, we will randomize a total of 375 participants (125 per group).

Buprenorphine adherence. We expect a fairly large difference in buprenorphine adherence between the two Contingency Management groups and the Usual Care group. Specifically, we expect that each Contingency Management group will provide urine samples positive for buprenorphine on 85% of the assessments, whereas we expect that the Usual Care group will provide urine samples positive for buprenorphine on 45% of the assessments. Thus, we expect to obtain a 40% difference in buprenorphine adherence between each of the Contingency Management groups and the Usual Care group.

Opiate abstinence. We expect large differences in opiate abstinence between each of the two Contingency Management groups and the Usual Care group, but a relatively small difference in opiate abstinence between the two Contingency Management groups. The Power Analysis was designed to allow

Date: April 12, 2023

Principal Investigator: [name]

Application Number: IRB00220692

us to detect the smallest difference in opiate abstinence between groups: the difference between the Buprenorphine Adherence Only (expected 68% opiate negative) and the Buprenorphine Adherence and Opiate Abstinence (expected 83% opiate negative) groups; to detect this difference, we would need 106 participants.

Total sample size. Based on the analyses described above, we would need 106 participants per group to detect effects between the pairs of groups for the planned comparisons. After adjusting for the anticipated rates of missing data (15% missing), we need to randomize 125 participants to each of the three groups to ensure that we have sufficient sample sizes (125 participants x 0.85 collected assessments = 106 participants per group). Thus, we will randomize a total of 375 participants.

d. Early stopping rules.

The study investigators and a Data Monitoring Committee (DMC) will provide data and safety monitoring of the proposed trial. To monitor adverse events, all staff members who have regular contact with study participants are instructed on the need to report to an investigator any indication that an adverse event has occurred. When the staff members and investigators learn of an adverse event, they will investigate until they have determined as many of the relevant details of the adverse event as possible. To provide consistent monitoring of adverse events across groups, participants will be asked about all categories of adverse events at each routine assessment visit conducted throughout the study. At least one investigator will review each adverse event as it occurs. The DMC will review a summary of adverse events annually. This frequency of review will be increased if the adverse events occur at a higher rate than anticipated. The protocol can be stopped based on recommendations of the investigators or DMC who are reviewing the adverse events in the study. We will ask the investigators and DMC to recommend that the trial be stopped if a review of the adverse events suggests to any of the investigators or DMC members that the number of related adverse events is unacceptably high. The investigators or DMC will be allowed to request statistical analyses to compare the groups on the rates of different adverse events or to have the adverse event data summarized in other ways that they deem appropriate.

8. Risks

a. Medical risks, listing all procedures, their major and minor risks and expected frequency.

This study involves the development and evaluation of a behavioral intervention to promote adherence to an FDA-approved medication (buprenorphine) for opioid use disorder. The study poses little risk to participants and offers the potential of substantial benefit. There is essentially no risk above those of normal daily living associated with the incentives, or with the data collection procedures in this study.

b. Steps taken to minimize the risks.

To protect confidentiality, all research participants are identified by participant identification codes (Participant IDs) consisting of their initials and sequentially-assigned participant numbers on most forms and data files, and not by their names. All research data are stored in locked areas accessible only to research staff and are not left unattended. Documents with confidential information are shredded before being discarded. Confidential information is never given to anyone outside of the research program without the explicit written permission of the research participant. Only selected designated staff members are approved to give confidential information out after obtaining explicit written permission from the participant. All research staff are trained in these procedures. We collect only general information about participant activities, legal and illegal. We do not collect information about specific illegal acts. Finally and importantly, the study smartphone app that will be used to provide monitoring and incentives has features that promote compliance with HIPAA.

Date: April 12, 2023

Principal Investigator: [name]

Application Number: IRB00220692

To protect against suicide risk, participants will be routinely screened for suicidal ideation using the question “In the past 30 days, have you experienced serious thoughts of suicide?” on the ASI-Lite at each study assessment. If a participant shows any indication that he/she might be at risk for suicide at any point during the study, a staff member will remain with an at-risk participant until an appropriate healthcare professional takes responsibility for the participant. The staff member will immediately notify the study clinician and the Principal Investigator upon learning of the suicide risk. The participant will be seen by the study clinician, who will assess the risk of suicide and determine the appropriate course of action. If a participant indicates that he/she is at risk for suicide over the phone, staff will call 911 and stay on the phone with the participant until the police arrive. Our research team is trained to implement and has experience implementing these procedures.

To protect against overdose risks, all participants will be offered referrals to the Baltimore City Health Department’s Staying Alive Program, which teaches drug users how to avoid opioid overdoses and how to respond in the event of an opioid overdose emergency. At each study assessment, we will provide participants with the Center for Disease Control and Prevention’s pamphlet on preventing an opioid overdose (<https://www.cdc.gov/drugoverdose/pdf/patients/Preventing-an-Opioid-Overdose-Tip-Card-a.pdf>), which includes overdose risk factors, signs and symptoms, and bystander response to overdose.

c. Plan for reporting unanticipated problems or study deviations.

Unanticipated problems or study deviations will be reported based on the guidelines of the Johns Hopkins University School of Medicine IRB.

d. Legal risks such as the risks that would be associated with breach of confidentiality.

There are risks that the confidential information we collect could be revealed to people not involved in the research such as a friend, relative, or an outside organization. This could be embarrassing to the participant if the participant wanted to keep participation in the study secret. We do not collect information about specific illegal acts. Thus, the risks associated with the assessments are not greater than the risks associated with routine psychological examinations or tests.

e. Financial risks to the participants.

There are no financial risks above those of normal daily living. Each participant is responsible for ensuring that the earnings are reported properly to relevant government or private agencies and for determining whether or not the earnings will affect any benefits they might receive from those agencies.

9. Benefits

a. Description of the probable benefits for the participant and for society.

Participants in the experimental groups will receive access to our customized mobile-health application that could improve buprenorphine treatment. If the proposed intervention is an effective means of promoting buprenorphine treatment engagement and adherence, it could reduce the substantial morbidity, mortality, and societal healthcare costs associated with opioid use disorder.

10. Payment and Remuneration

a. Detail compensation for participants including possible total compensation, proposed bonus, and any proposed reductions or penalties for not completing the protocol.

All incentives in this study will be provided by giving participants reloadable credits and adding incentives to the card when earned. We have been using these reloadable credit cards in our ongoing research and they have proved attractive to participants and convenient for staff to manage.

Date: April 12, 2023

Principal Investigator: [name]

Application Number: IRB00220692

Incentives for participating in the 7-day induction period. Participants will be invited to participate in a 7-day induction period. Participants may earn up to \$70 for participating in the induction period.

Incentives for completing study group instructions. Participants will be paid \$50 for completing study instructions that will teach them about the details of their study group.

Incentives for completing routine assessments for both groups. Outcome assessments will be conducted at intake, every month during the 3-month intervention period, and at 6, 9, and 12 months after randomization. Participants will be paid \$50 for completing each of the intake and monthly assessments, and \$100 for completing each of the follow-up assessments. In total, participants can earn \$500 for completing these assessments.

Participant referral fees. Participants will have the optional opportunity to earn incentives for referring people who are interested in the study. If a referral attends the initial screening and completes the necessary assessments, the participant who referred the person will receive up to \$20. If a referred person enrolls in the main study, the participant who referred the person will receive up to \$40 for the referral.

Contingency management for facilitating buprenorphine adherence. Participants in the Buprenorphine Adherence and Opiate Abstinence group and the Buprenorphine Adherence Only group will be able to earn \$10 per day for taking their buprenorphine dose and submitting a valid video recording of administration before midnight. Over the entire 3-month study period, participants in these groups could earn \$910 for adhering to buprenorphine treatment.

Contingency management for opiate abstinence. Participants in the Buprenorphine Adherence and Opiate Abstinence group will be able to earn \$10 per day for providing opiate-negative saliva samples and submitting a valid video recording of saliva drug testing. Over the entire 3-month study period, participants in this group could earn \$910 for providing opiate-negative saliva samples.

11. Costs

a. Detail costs of study procedure(s) or drug (s) or substance(s) to participants and identify who will pay for them.

There will be no costs to participants for any services or treatment provided in this study.

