Buprenorphine Adherence and Opiate Abstinence and Buprenorphine Adherence Only participants will receive incentives for daily buprenorphine use. Buprenorphine Adherence and Opiate Abstinence participants also will receive incentives for providing opiate-negative saliva samples. Daily buprenorphine use and opiate abstinence will both be remotely verified using smartphone-enabled video directly observed therapy (Video DOT) provided by emocha Mobile Health, Inc. The incentives will be integrated into the Video DOT platform and delivered remotely to reloadable credit cards. Participants will be assessed every month during a 3-month intervention period and every 3 months during a 9-month follow-up period. The primary outcome measures will be a) opiate abstinence and b) buprenorphine adherence during the 3-month intervention as assessed by urinalysis results every month during the intervention. If the proposed intervention is effective, it could improve patients' access to and success in office-based buprenorphine treatment.

2. Objectives (include all primary and secondary objectives)

Primary Aims

- Determine effectiveness of Contingency Management compared to Usual Care in promoting buprenorphine adherence and opiate abstinence as assessed by urine drug screens during the intervention.

Secondary Aims

- Determine effectiveness of Contingency Management compared to Usual Care in: a) reducing buprenorphine diversion, b) promoting retention in buprenorphine treatment, c) reducing opioid overdose and risk of overdose, d) improving psychosocial functioning and quality of life, e) promoting patient treatment satisfaction, and f) maintaining any effects after the intervention period ends.

3. Background (briefly describe pre-clinical and clinical data, current experience with procedures, drug or device, and any other relevant information to justify the research)

Opioid use has increased to epidemic levels in the United States and is a major cause of morbidity and mortality nationwide.¹⁻⁴ In 2016 alone, more than 42,000 people died from an overdose involving

Date: April 12, 2023

Principal Investigator: [name]

Application Number: IRB00220692

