Validation of video of buprenorphine administration and saliva testing. By 4:00 PM on the day after a participant submits a video, or Monday if the participant submitted the video on Friday or Saturday, a staff member will review the videos. The validation process will occur on a staff computer using the provider-facing web portal. First, the program will display a previously obtained photo of the participant alongside the video to confirm that the correct person provided the video. The staff member will confirm that the person in the video matches the photo of the participant. If the person in the video matches the photo of the participant, the staff member will view the video to determine if the participant correctly administered his/her buprenorphine dose, or to determine if the participant provided a valid, opiate-negative saliva sample, if applicable. Participants will be able to visualize their earnings over time on a dashboard within the application.

Contesting the validation decision. Participants will be able to contest the validation decision of a staff monitor. Participants will be taught how to contest the validation decision during the in-person training and can see the decisions made on their video submissions from the application. All contested videos will be viewed by an independent staff member that was not involved in the original video validation.

Reloadable Credit Cards. At the start of enrollment, each participant will be given a reloadable credit card. Any incentive earnings will be added to the card. Each card can then be used as a regular credit card to make purchases at most businesses. We currently use this reloadable credit card system in our ongoing incentive programs, and it has proven very efficient and highly acceptable to participants.

Usual Care Control Group

Participants assigned to the Usual Care group will receive routine office-based buprenorphine treatment at their treatment programs. The primary rationale for selecting this control group is to maximize clinical applicability and generality of study results by evaluating office-based buprenorphine treatment as it is typically delivered. The issue this study addresses is what clinical benefit is achieved by adding two different intensities of Contingency Management to office-based buprenorphine. Our Usual Care group will

Date: April 12, 2023

Principal Investigator: [name]

Application Number: IRB00220692

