determine the percentage of the study population that will adhere to buprenorphine treatment and maintain opiate abstinence under routine conditions.

Buprenorphine Adherence Only Group

Participants assigned to the Buprenorphine Adherence Only group will receive financial incentives for promoting daily buprenorphine use for 3 months. Participants will be able to earn \$10 per day for taking their buprenorphine dose and submitting a valid video recording of administration before midnight. If a participant fails to submit a video or if a submitted video is deemed invalid, the participant will not receive the scheduled incentive that day and the daily incentive value will be decreased to \$3 per day. Then, the amount earned per day will increase to \$10 per day after the participant submits a valid video of buprenorphine administration every day for seven days.

Buprenorphine Adherence and Opiate Abstinence Group

Similar to the Buprenorphine Adherence Only group, this group will receive financial incentives for promoting daily buprenorphine use using the procedures described above. However, to reduce or eliminate the opiate use that we expect will persist in participants in the Buprenorphine Adherence Only group, this group also will receive financial incentives for opiate abstinence. Participants will be asked to provide saliva samples according to a random, and then progressively more intermittent drug-testing schedule. Participants will receive an in-app notification each day stating whether or not it is a mandatory collection day. Initially, participants will be required to provide three saliva samples per week, on average. After 30 days in which all mandatory samples meet the abstinence criteria, participants will be required to provide two saliva samples per week, on average. After an additional 30 days in which all mandatory samples meet the abstinence criteria, participants will be required to provide one saliva sample per week, on average.

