Assessments will be conducted at intake, every month during the 3-month intervention period, and at 6, 9, and 12 months after randomization. Participants will be paid \$50 for completing each of the intake and monthly assessments, and \$100 for completing the follow-up assessments. These assessments will be collected using REDCap. Whenever possible, assessments will be conducted remotely via phone or web-conferencing.

Intake Only Assessment Instruments

DSM-5 Checklist for Opioid Use Disorder. The DSM-5 checklist for opioid use disorder is a structured assessment that will be used to determine if participants have opioid use disorder.

Non-Study Medical and Other Services – NSMOS-BL. This assessment will be used to collect information on medical services participants may have received in the 3 months prior to study intake.

Intake and Major Assessment Instruments

Urine and saliva toxicology testing. Urine and saliva samples will be collected and tested for opioids and other drugs. Toxicology testing may be conducted by sending a testing kit to participants through the mail. Participants would then be asked to complete the toxicology tests (urine and saliva) and provide a video showing the results of the tests using the study smartphone app.

Time-line follow-back (TLFB). Participants will be asked whether or not they are in treatment for their opioid use disorder, including treatment other than buprenorphine (e.g., methadone maintenance). For participants who report being in buprenorphine treatment, the TLFB procedure will be used to elicit participants' self-reported taking of their buprenorphine dose each day. Pharmacy and/or clinic records (with participant permission) may be used to confirm self-reported data.

Opioid Overdose Risk Assessment. An opioid overdose risk assessment will be used to assess the rate at which participants report engaging in behaviors that may put them at risk for an opioid overdose.

The Addiction Severity Index – Lite (ASI-Lite). The ASI-Lite is a structured interview designed to assess problem severity in areas commonly affected by drug and alcohol use (medical, legal, employment, family/social, and psychiatric) with good reliability and validity.

Smartphone Form. This questionnaire will document participants' access to and willingness to use a smartphone during the study.

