c. Blinding, including justification for blinding or not blinding the trial, if applicable.

Participants will not be blinded as to their study condition because participants in the incentive intervention cannot be blind to that intervention.

d. Justification of why participants will not receive routine care or will have current therapy stopped.

N/A

e. Justification for inclusion of a placebo or non-treatment group.

N/A

f. Definition of treatment failure or participant removal criteria.

Participants will be removed from the study if they threaten the safety of staff or other research participants, or of any other persons on the Johns Hopkins Bayview Campus.

g. Description of what happens to participants receiving therapy when study ends or if a participant's participation in the study ends prematurely.

Throughout the study, participants will be given referrals to services they might need (e.g., drug counseling, housing, medical, or employment services). Participants will continue to receive buprenorphine treatment as long as that treatment is available in the program they attend.

5. Inclusion/Exclusion Criteria

Applicants will be invited to participate in this study if they: a) are \geq 18 years old, b) meet DSM-5 criteria for opioid use disorder, c) are enrolled in buprenorphine treatment, and d) use the smartphone

Date: April 12, 2023

Principal Investigator: [name]

Application Number: IRB00220692

application to record and submit videos on 6 or more days during the 7-day induction period. Applicants will be excluded if they: a) have current suicidal/homicidal ideation, or b) are unwilling or unable to use a smartphone.

6. Drugs/ Substances/ Devices

a. The rationale for choosing the drug and dose or for choosing the device to be used.

N/A

b. Justification and safety information if FDA approved drugs will be administered for non-FDA approved indications or if doses or routes of administration or participant populations are changed.

N/A

c. Justification and safety information if non-FDA approved drugs without an IND will be administered.

N/A

7. Study Statistics

We will compare the three study groups on primary and secondary outcome measures.

a. Primary outcome variable.

Buprenorphine Adherence. We will assess the percentage of participants with buprenorphine-positive urine samples at the monthly assessments during the 3-month intervention evaluation period (Yes/No at each assessment).

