Opiate Abstinence. We will assess the percentage of participants with opiate-negative urine samples (excluding buprenorphine and methadone if self-report confirms that the participant is enrolled in buprenorphine or methadone treatment) at the monthly assessments during the 3-month intervention evaluation period (Yes/No at each assessment).

b. Secondary outcome variables.

Buprenorphine Diversion. We will assess the number of days participants report diverting their daily buprenorphine dose (selling or giving their buprenorphine dose to someone else) during the 28 days prior to each of the monthly assessments during the 3-month intervention evaluation period (based on TLFB).

Retention in Buprenorphine Treatment. We will assess the last day that participants reported taking buprenorphine during the 3-month intervention evaluation period (based on TLFB).

Overdose risk. We will assess the rates at which participants report engaging in overdose risk behaviors at the monthly assessments during the 3-month intervention evaluation period (based on total scores from the opioid overdose risk assessment).

Psychosocial Functioning. We will assess patient-reported psychosocial functioning during the 3-month intervention evaluation period (based on the ASI-Lite).

Quality of Life. We will assess patient-reported quality of life during the 3-month intervention evaluation period (based on scores from the SF-36).

Patient Treatment Satisfaction. We will assess patient-reported treatment satisfaction during the 3-month intervention evaluation period (based on scores on the CSQ-8).

Post-Intervention Effects. We will assess the outcomes described above every 3 months during a 9-

Date: April 12, 2023

Principal Investigator: [name]

Application Number: IRB00220692

month follow-up after the intervention ends.

c. Statistical plan including sample size justification and interim data analysis.

Statistical Analyses

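### Diversion is measured only by self-report from participants who know their group, and only the incentive groups are paid for dosing, so under-reporting of diversion on paid days could favour the intervention

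*Combined protocol and SAP*

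**What the plan says.** Section 2 lists "reducing buprenorphine diversion" as secondary aim (a), comparing Contingency Management with Usual Care. Section 7.b defines the outcome: "We will assess the number of days participants report diverting their daily buprenorphine dose", counted over the 28 days before each monthly assessment and based on the TLFB. Section 4.a describes the TLFB as eliciting "self-reported taking of their buprenorphine dose each day" and adds: "Pharmacy and/or clinic records (with participant permission) may be used to confirm self-reported data". On the mode of assessment it says: "Whenever possible, assessments will be conducted remotely via phone or web-conferencing".

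On payment, section 4.a gives both incentive groups $10 a day for a dose taken and shown on a valid video. Otherwise, "if a submitted video is deemed invalid, the participant will not receive the scheduled incentive that day", and the rate falls to $3 until seven straight days of valid videos restore it. Research staff decide validity: "a staff member will review the videos", checking identity and correct administration. Section 10 puts the maximum for adherence at $910. Usual Care participants receive routine treatment and no payment for dosing.

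On blinding, section 4.c says: "Participants will not be blinded as to their study condition because participants in the incentive intervention cannot be blind to that intervention". It does not mention the people who collect outcomes. Section 7.c plans longitudinal logistic models for the secondary measures, adjusted for the stratification covariates. Its sensitivity work concerns missing values only.

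**The concern.** Diversion is one of the three limitations of office-based buprenorphine that the abstract gives as the reason for the trial. It is measured only by what the participant chooses to disclose. In the incentive groups, the same research program that asks about diversion also pays for dosing, day by day. The TLFB is also day by day, so an answer can contradict a day that was paid. The assessments at months 1 and 2 fall while earnings continue, and nothing tells participants that their answers do not count against them. A perceived stake is enough to discourage disclosure, and it exists in two of the three randomized groups only.

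Randomization does not remove a difference in reporting that arises after assignment and because of it, and adjustment for baseline covariates does not either. A lower reported count in the incentive groups could then be read as less diversion when some of it is less disclosure.

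**Working it through.** **Figures in the plan.** No rate, effect size or power is stated for diversion. The related figures reproduce: 91 days × $10 = $910, and 106 / 0.85 = 124.7, so 125 per group and 3 × 125 = 375. The 106 was derived for opiate abstinence and is used below only as a working group size.

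**Which diverted days carry a stake.** From the payment rules in section 4.a:

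| Group and day | Paid? | Does reporting diversion contradict a payment? |
|---|---|---|
| Incentive, no video | No | No |
| Incentive, video judged invalid | No | No |
| Incentive, video judged valid, dose partly or wholly passed on (a partial or faked dose) | Yes | Yes |
| Usual Care, any day | No payment exists | No |

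Only the third row differs from Usual Care. The mechanism therefore acts only on days that were both diverted and paid.

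**Size on the planned scale (days per 28).** Let D be true mean diversion days, equal in all groups (no true effect). Let r be the share of diverted days reported when no payment is at stake, w the share of incentive-group diverted days that were paid, and c the share of those, otherwise reportable, that are concealed.

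- Usual Care reported mean = D × r
- Incentive-group reported mean = D × r × (1 − w × c)
- Spurious relative reduction = w × c

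D and r cancel. The document gives neither w nor c, so both are assumed.

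**Size on an odds-ratio scale.** Section 7.c assigns logistic models to a count without naming a cut-off, so I take any versus no reported diversion at one visit. With true proportion p (assumed), the incentive-group reported proportion is q = p × (1 − w × c), where w × c is now the share of diverters who report none. The odds ratio is [q/(1 − q)] / [p/(1 − p)]. The chance of a false significant result favouring the intervention, with 106 per group and a two-sided 5% test, is Φ[(p − q − 1.96 × SE0) / SE1]. SE0 = √(2 × m × (1 − m)/106), with m the mean of p and q, and SE1 = √([p(1 − p) + q(1 − q)]/106).

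Worked case, p = 0.20 and w × c = 0.25: q = 0.15, and the odds ratio is (0.15/0.85)/(0.20/0.80) = 0.71. SE0 = 0.0522 and SE1 = 0.0521, so Φ(−1.00) = 15.8%.

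| w × c | Spurious cut in mean days | Odds ratio at p = 0.10 / 0.20 / 0.30 | False favourable result at p = 0.10 / 0.20 / 0.30 |
|---|---|---|---|
| 0 | 0% | 1.00 / 1.00 / 1.00 | 2.5% (nominal) |
| 0.10 | 10% | 0.89 / 0.88 / 0.86 | 4.3% / 5.6% / 7.0% |
| 0.25 | 25% | 0.73 / 0.71 / 0.68 | 9.4% / 15.8% / 23.5% |
| 0.50 | 50% | 0.47 / 0.44 / 0.41 | 28.1% / 53.2% / 74.7% |

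A product of 0.25 arises if half the diverted days were paid and half of those concealed. A product of 0.50 needs, for example, every diverted day to have been paid and half concealed, which is an extreme case. With half concealed, p = 0.20 and only a quarter or a tenth of reports affected, the odds ratio is 0.85 or 0.94.

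**The case against.** The strongest reply is that payment follows a video that staff have checked for identity and correct administration. A dose seen to be taken is hard to divert, so fewer reports in the incentive groups may simply be the effect the trial hopes for. This stands, and it is why the size cannot be fixed: w may be small, and at w = 0 the payment mechanism vanishes.

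A reader might go further than the document allows in three ways.

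- *That reporting any diverted dose admits an unearned payment.* It does not. A dose diverted on a day with no video, or an invalid one, was never paid.
- *That a TLFB answer could lower the daily rate or reverse a payment.* No passage says so. The fall to $3 is tied to missing or invalid videos. What remains is a perceived stake that nothing in the plan dispels.
- *That the interviewers are unmasked, or are the staff who validate videos.* Section 4.c covers participants only, and the document does not say who administers the TLFB. Masking and separation of roles are unstated, not shown to be absent.

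Three safeguards could also be cited. Pharmacy or clinic records are optional and need permission, and they would show dispensing or attendance rather than what was done with a dose. The monthly buprenorphine urine test applies to all groups, but a positive result does not exclude diversion on some of the 28 days. The confidentiality rule in section 8.b restricts release outside the research program; it does not stop video reviewers inside it from seeing answers. None of these removes the problem.

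**Conclusion.** The concern holds in a limited form. During the 3-month intervention, the diversion outcome is open to differential under-reporting, with a likely direction that favours the incentive groups, and nothing planned would detect it. It would be tempting to call the diversion comparison biased. The document does not support that, because a real reduction would look the same in these data. The inability to tell the two apart is the defect.

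The size is unknown. The tabulated figures rest on assumed shares and on no true effect, and they run from nothing at w × c = 0 upwards as more diverted days were paid and concealed. The payment stake ends with the intervention, so it does not apply in the same way to the follow-up reports. The primary outcomes, which come from urine tests, are not affected by this point. The case for acting is that the remedy is nearly free, not that the bias is proven.

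**What to change.** 1. At every assessment, in all three groups, open the TLFB diversion question with the same scripted statement: answers do not affect earnings and are not seen by the staff who validate videos or by the prescriber. Make this true with REDCap access rights, and state in the protocol who collects the TLFB.
2. Keep the 28-day TLFB count as the outcome.
3. State in the analysis plan that a lower reported count during the intervention cannot by itself separate less diversion from less disclosure. Read it alongside the diversion reports at 6, 9 and 12 months, collected after payments end. A difference that persists is harder to attribute to the payment stake. A difference that disappears fits either explanation, since a real effect may also fade.
4. If the item is made self-completed instead, skipped answers become an issue. Section 7.c imputes missing values as the adverse outcome, so a skipped item would count as diversion. Do not apply that rule to this item without also reporting the result without imputation.

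The cost is one script, one access setting and a slightly more cautious conclusion. If data collection has finished, step 3 is still available.
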